5. PATIENT ELIGIBILITY

Patients will be included in the study based on the following inclusion and exclusion criteria.

INCLUSION CRITERIA

1. Patient must have cholangiocarcinoma, gallbladder cancer or adenocarcinoma on liver biopsy with clinical features consistent with biliary primary/ cholangiocarcinoma.
2. Metastatic or unresectable disease documented on diagnostic imaging studies.
3. Must have received at least one regimen containing gemcitabine chemotherapy.
4. Eastern Cooperative Oncology Group (ECOG) Performance Status of 0 to 1 (Appendix 1).
5. The patient has adequate hepatic function as defined by a total bilirubin ≤ 1.5 mg/dL (25.65 $\mu\text{mol/L}$), and aspartate transaminase (AST) and alanine transaminase (ALT) ≤ 3.0 times the upper limit of normal (ULN; or 5.0 times the ULN in the setting of liver metastases).
6. The patient has adequate hematologic function, as evidenced by an absolute neutrophil count (ANC) $\geq 1000/\mu\text{L}$, hemoglobin ≥ 9 g/dL (5.58 mmol/L), and platelets $\geq 100,000/\mu\text{L}$.

7. The patient does not have:
 - a. Cirrhosis at a level of Child-Pugh B (or worse) or
 - b. Cirrhosis (any degree) and a history of hepatic encephalopathy or clinically meaningful ascites resulting from cirrhosis. Clinically meaningful ascites is defined as ascites from cirrhosis requiring diuretics or paracentesis.
8. The patient has adequate renal function as defined by a serum creatinine ≤ 1.5 times the ULN, or creatinine clearance (measured via 24-hour urine collection) ≥ 40 mL/minute (that is, if serum creatinine is > 1.5 times the ULN, a 24-hour urine collection to calculate creatinine clearance must be performed).
9. The patient's urinary protein is $\leq 1+$ (≤ 30 -100 mg/dl) on dipstick or routine urinalysis (UA; if urine dipstick or routine analysis is $\geq 2+$ (≥ 100 -300 mg/dl), a 24-hour urine collection for protein must demonstrate < 1000 mg of protein in 24 hours to allow participation in this protocol).
10. The patient must have adequate coagulation function as defined by International Normalized Ratio (INR) ≤ 1.5 and a partial thromboplastin time (PTT) (PTT/aPTT) $< 1.5 \times$ ULN.). Patients on full-dose anticoagulation must be on a stable dose (minimum duration 14 days) of oral anticoagulant or low molecular weight heparin. If receiving warfarin, the patient must have an INR ≤ 3.0 and no active bleeding (that is, no bleeding within 14 days prior to first dose of protocol therapy) or pathological condition present that carries a high risk of bleeding (for example, tumor involving major vessels or known varices).
11. Because the teratogenicity of ramucirumab is not known, the patient, if sexually active, must be postmenopausal, surgically sterile, or using effective contraception (hormonal or barrier methods).
12. Female patients of childbearing potential must have a negative serum pregnancy test within 7 days prior to enrollment.
13. Patients must sign an Informed Consent and Authorization indicating that they are aware of the investigational nature of this study and the known risks involved.
14. Patient is ≥ 18 years of age on the day of consenting to the study.
15. In the ten patient expanded cohort, patients diagnosed with DNA repair or FGFR genetic aberrations will be enrolled.

EXCLUSION CRITERIA

1. The patient has experienced any Grade 3-4 GI bleeding within 3 months prior to enrollment.

2. Prior therapy with any agent targeting the VEGFR pathway to include bevacizumab, pazopanib, and other anti-angiogenesis inhibitors.
3. The patient has a history of deep vein thrombosis, pulmonary embolism, or any other significant thromboembolism, including portal venous thrombosis (venous port or catheter thrombosis, incidental pulmonary embolism diagnosed on imaging studies or superficial venous thrombosis are not considered “significant”) during the 3 months prior to randomization.
4. The patient has experienced any arterial thromboembolic events, including but not limited to myocardial infarction, transient ischemic attack, cerebrovascular accident, or unstable angina, within 6 months prior to enrollment.
5. The patient has uncontrolled or poorly-controlled hypertension (>160 mmHg systolic or > 100 mmHg diastolic for >4 weeks) despite standard medical management.
6. The patient has a serious or non-healing wound, ulcer, or bone fracture within 28 days prior to enrollment.
7. The patient has undergone major surgery within 28 days prior to enrollment, or subcutaneous venous access device placement within 7 days prior to enrollment.
8. The patient is receiving chronic antiplatelet therapy, including aspirin, nonsteroidal anti-inflammatory drugs (NSAIDs, including ibuprofen, naproxen, and others), dipyridamole or clopidogrel, or similar agents. Once-daily aspirin use (maximum dose 325 mg/day) is permitted.
9. The patient has elective or planned major surgery to be performed during the course of the clinical trial.
10. The patient is pregnant or breast-feeding.

6. TREATMENT PLAN

This is an open-label phase II study. Patients with advanced biliary cancers will be enrolled. All patients must be registered on the M. D. Anderson Cancer Center Clinical Oncology Research (CORE) system prior to initiation of treatment.

This study will enroll up to 60 patients to at MD Anderson Cancer Center. Accrual is projected to be 2.5 subjects per month. If this study proceeds to a future trial for patients with DNA repair gene of FGFR mutations, data obtained from this expanded cohort of 10 patients will be included in final analysis.

This will be an open-label, single arm study with each cycle being 14 days. Ramucirumab will be administered at 8 mg/kg intravenously on day 1 of the cycle. Restaging will be done every 4 cycles (+/- 1week). Treatment will be continued until progression unless other reasons for study discontinuation occur as listed in section 8 “Criteria for Removal from the Study.” Additionally, patients who have therapy interrupted for consolidative therapies (including, but not limited to radiation therapy, radioembolization, and chemoembolization) or at the physician’s discretion, will remain on study for survival analyses.

Table 2: Starting Dose Level

Drug	Dose	Infusion Time	Schedule (in 14-day cycle)
IV Ramucirumab	8 mg/kg	60 min (+/- 5 min)	Day 1

Dosing and Administration

The study drug will be provided by the sponsor and administered in the following order with the specified pre-medications:

- Premedication should be with an IV H₁ agonist, diphenhydramine 50 mg in NS 50 mL IV within 30 minutes prior to treatment
- Ramucirumab 8 mg/kg in NS to final volume of 250 mL IV over 60 minute on day 1 repeated every 14 days

Dose Modifications and Toxicity Management

Dose modifications and treatment delays based on observed drug-related toxicity will be performed as described below. Any toxicity associated or possibly associated with ramucirumab treatment should be managed according to standard medical practice.

Specific adverse events of concern, which may or may not be associated with ramucirumab therapy, include infusion reactions, hypertension, arterial or venous thrombotic events, bleeding (hemorrhagic) events, and proteinuria. These are specified in greater detail below.

A cycle of therapy may be delayed up to 3 weeks to allow for weather events, patient’s personal emergencies, observation of holidays, or other unforeseen delays that the Investigator deems to be in the best interest of the patient. For any dose interruptions, re-initiation of therapy may be delayed for a maximum of 30 days to allow recovery from any toxicity. In exceptional cases where subjects are responding, re-initiation of therapy after missing > 30 consecutive days of treatment may be done on a case-by-case basis after confirmation with the Primary Investigator.

Toxicity will be graded according to the NCI CTCAE, Version 4.0 (which is available at: http://ctep.info.nih.gov/protocolDevelopment/electronic_applications/ctc.htm). For any event which is apparent at baseline, the dose modification will apply according to the corresponding shift in toxicity grade if the investigator feels this is appropriate, (e.g. if a patient has grade 1 asthenia at baseline which increases to grade 2 during treatment, this will be considered as a shift of 1 grade and treated as a grade 1 toxicity for dose modification purposes).

Dose modifications of ramucirumab will be done based on the specific toxicity. Once a dose of

any study drug has been reduced, it should not be increased at a later time. Reasons for dose modifications or delays, the supportive measures taken, and the outcome will be documented in progress notes. Growth factors may be used to treat hematologic toxicity and will not constitute a dose reduction. A maximum of a 3-week treatment delay is permitted to allow recovery of toxicities.

Table 3: Dose Levels

Dose Level	Ramucirumab (mg/kg)
0 – baseline	8
-1	6
-2	5

Hematologic Toxicity

Though myelosuppression is expected to be rare, in the event dose modifications are required at the beginning of a cycle due to hematologic toxicities, dose of ramucirumab may be adjusted as detailed below.

Table 4: Dose Modifications for Day 1 of Each Cycle (Hematologic Toxicity)

ANC		Platelets	Timing
≥ 1,500 cells/mm ³	AND	≥ 75,000/uL	Treat on time
< 1,500 cells/mm ³	OR	< 75,000/uL	Delay by 1 week intervals until recovery

Special Instructions Regarding Treatment of Chemotherapy-related Toxicity

Dose modification or delay may occur in the setting of lower Grade toxicity if the treating physician believes that it is in the interest of a subject’s safety. Alopecia and nausea and/or vomiting that can be controlled by antiemetics do not require dose modification or interruption. No dose reduction or interruption will be required for anemia as it can be satisfactorily managed by transfusions. Dose reductions for non-hematologic toxicity should be as below.

Table 5: Dose Modifications for Ramucirumab on Day 1 of Each Cycle (Non-Hematologic Toxicity)*

Toxicity/Dose Held	Ramucirumab dose this cycle
Grade 0-2 toxicity	Same as Day 1 previous cycle
Grade 3 toxicity	Decrease ramucirumab to next lower dose level
Grade 4 toxicity	Off protocol treatment
Dose held in 2 previous consecutive cycles	Decrease ramucirumab to next lower dose level and continue throughout the rest of treatment

* Drug-specific toxicities are explained in greater detail below with appropriate modifications

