Ramucirumab is a fully human IgG1 monoclonal antibody that is a specific and direct inhibitor of VEGFR-2, where it binds to the extracellular VEGF-binding domain with high degree of specificity and affinity, at picomolar dose range. It thus prevents the binding of the VEGF ligand to the VEGF-R2 receptor. In the phase I trial for patients with advanced solid tumors, ($n=37$) ramucirumab demonstrated encouraging early evidence of efficacy at a range of dose levels including the one enrolled patient with biliary cancer who experienced stable disease lasting over 5 months³⁰. Ramucirumab was recently shown to improve survival compared with placebo in advanced gastric cancer, with a median overall survival of 5.2 months in the ramucirumab arm, and 3.8 months in the placebo arm. The main toxicity seen was an increase in hypertension in the ramucirumab group³¹. Additionally, a double-blind, randomized, phase III study of previously treated gastric and gastroesophageal junction cancers included 665 patients randomized to ramucirumab plus paclitaxel versus placebo plus paclitaxel³². In this study, the combination arm showed an improvement in overall survival (9.6 months vs. 7.4 mths, $p=0.017$), providing further rationale for the use of ramucirumab in refractory gastric cancer.

Initial data with ramucirumab in biliary cancer

In the initial 43 patient cohort that was enrolled in this phase II trial, 42 patients with cholangiocarcinoma and gallbladder cancers received treatment. Ramucirumab was well tolerated with 9 grade 3 toxicities including anorexia, dehydration, hypertension, hyponatremia, proteinuria and vomiting. There were no grade 4 toxicities. The median PFS for all patients who received treatment was 2.73 months (95% CI 1.91-8.03 months) and median OS was 6.31 months (95% CI 4.7 months – not reached). The overall response rate was 0% and disease control rate (SD + PR + CR) was 44%. Importantly, 6 patients (13%) were on treatment for > 24 weeks. Of these, 3 were on treatment for at least 44 weeks. In reviewing the genomic data on the 6 patients with prolonged periods of stable disease, we noted that 4 of the 6 harbored mutations in DNA repair pathways (BRCA, FANCA, ARID1A) and 1 patient had an FGFR alteration

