4. OBJECTIVES

PRIMARY

Determine the progression-free survival (PFS) of ramucirumab in advanced biliary cancers (intrahepatic cholangiocarcinoma, extrahepatic cholangiocarcinoma, and gallbladder cancer) who have received prior chemotherapy.

SECONDARY

- Determine the response rate (RR) and disease control rate (partial response + complete response + stable disease) of ramucirumab in advanced biliary cancers
- Determine overall survival (OS) of ramucirumab in advanced biliary cancers
- Evaluate the toxicity of ramucirumab in advanced biliary cancers

EXPLORATORY

- Correlate the carbohydrate antigen (CA) 19-9 response (defined as >50% decrease from baseline) with tumor response, PFS and OS
- Correlate baseline tumor gene expression profile with PFS
- Correlate pre- and post-therapy CT imaging to quantify iodine content, atomic numbers, and Z-values and correlate with response

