10. STATISTICAL METHODS

10.1 Study design and sample size

This is a single arm, open label, phase II trial to assess the efficacy and toxicity of ramucirumab in patients with pre-treated, advanced bile duct cancer. The primary objective is to evaluate the efficacy of the therapy. The primary endpoint is the progression-free survival (PFS). A maximum of 60 patients will be enrolled in the study at an estimated accrual rate of 2-3 patients per month. The study will monitor for futility and safety so that it will stop early if based on the interim data, it is unlikely the PFS will be better than that estimated from historical data or the study drug is too toxic.

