10.2 Primary efficacy endpoint

The primary endpoint is PFS, which is calculated as the time period from the date of treatment start to the date of disease progression or to the date of death, whichever occurs first, or to the last follow-up date if patients are alive without disease progression. It is expected that the median PFS time will be 3 months or more under this study treatment. If the trial continues to accrual of 60 patients and maintains sufficient follow-up to observe 35 events (PD/death) with a median PFS of 3 months, then the 95% credible interval for the median PFS would extend from 2.1 to 4.2 months.

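### Section 10 gives no analysis rule for the ten marker-selected patients, so its single median PFS pools them by default; Tables 11 and 12 are computed for 50 patients, not the stated 60

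*Combined protocol and SAP*

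**What the plan says.** The primary objective (Section 4) is to "Determine the progression-free survival (PFS) of ramucirumab in advanced biliary cancers" after prior chemotherapy, with no marker restriction. Section 2, under the initial data with ramucirumab, reports results already seen: "In the initial 43 patient cohort that was enrolled in this phase II trial", 42 were treated and the median PFS was 2.73 months. Six patients stayed on treatment beyond 24 weeks, and "4 of the 6 harbored mutations in DNA repair pathways (BRCA, FANCA, ARID1A) and 1 patient had an FGFR alteration".

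Inclusion criterion 15 (Section 5) then states: "In the ten patient expanded cohort, patients diagnosed with DNA repair or FGFR genetic aberrations will be enrolled". Section 6 is the only place that speaks of analysing them: "If this study proceeds to a future trial for patients with DNA repair gene of FGFR mutations", then "data obtained from this expanded cohort of 10 patients will be included in final analysis". It does not name the trial whose analysis is meant, or say what happens if no further trial follows.

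In Section 10.1, "A maximum of 60 patients will be enrolled in the study". Section 10.2 gives a 95% credible interval of 2.1 to 4.2 months for 35 events at a 3-month median, opening with "If the trial continues to accrual of 60 patients". Section 10.6 plans one Bayesian posterior median PFS. It also plans a log-rank test between groups that it does not define. Nothing in Section 10 mentions the ten patients, DNA repair or FGFR. The patient counts in Tables 11 and 12 do not exceed 50, and the listed toxicity boundaries end at 18/45.

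**The concern.** The ten are selected on a marker that drew attention because carriers in this same trial had long disease control. Section 10 neither separates nor excludes them, so an analyst who follows it will put every enrolled patient into one median. That median then describes a population with more carriers than the objective's population. The study is open-label and single-arm, and its initial PFS result is already known. A written rule on who counts is therefore the main protection for the primary estimate.

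The second issue is coverage of the monitoring rules. If the study may enrol 60, operating characteristics and boundaries that stop at 50 do not describe the stated design, and it is unclear whether the futility and toxicity rules apply to the ten.

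**Working it through.** **1. Carrier share.** Section 2 identifies at least 4 + 1 = 5 carriers among 42 treated, taking the FGFR patient as separate from the four. That is 5/42 = 12%. Adding ten carriers, all treated, gives 15/52 = 29%. Carrier status is not reported for the other 36, so both shares are minimums. In general, c carriers move the share from c/42 to (c + 10)/52. With c = 21, for example, it goes from 50% to 31/52 = 60%. The share rises for any c below 42; only the amount is uncertain.

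**2. Possible shift in the median (illustration only).** Assume exponential PFS, an unselected median of 2.73 months, and 50 unselected plus 10 selected patients with median m. The documents give no m, so a range is shown. The true mixture median t solves [50 × 0.5^(t/2.73) + 10 × 0.5^(t/m)]/60 = 0.5. With full follow-up, a single-exponential model returns (50 × 2.73 + 10m)/60.

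| m (months) | Mixture median | Single-exponential model |
|---|---|---|
| 2 | 2.59 | 2.61 |
| 2.73 | 2.73 | 2.73 |
| 4.5 | 2.95 | 3.02 |
| 6 | 3.06 | 3.27 |
| 12 | 3.28 | 4.28 |

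With censoring 6 months after the last entry (20,000 simulated trials, 42 or 50 unselected), the pooled posterior median is about 2.5 for m = 1.5, 3.0-3.1 for m = 6 and 3.3-3.4 for m = 12, against about 2.7 without the ten. The half-width of the 10.2 interval is (4.2 - 2.1)/2, about 1 month. Only the full-follow-up model at a large m exceeds it.

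**3. The interval in 10.2.** The Section 10.3 prior IG(2.5625, 4.6875) with d events and total follow-up consistent with a 3-month median gives the posterior IG(2.5625 + d, 4.6875 + 3d). For d = 35, IG(37.5625, 109.6875) gives 2.17 to 4.14, within 0.1 month of the printed 2.1 to 4.2. The same formula gives 2.22-4.06 for d = 40, 2.25-3.99 for d = 45, 2.31-3.89 for d = 55 and 1.6-5.5 for d = 8.

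**4. Table 12.** The inputs are the beta(0.3, 0.7) prior, stopping when Pr(rate > 0.30) exceeds 0.9, and looks every 5 patients. The rule returns all nine printed boundaries. An exact binomial recursion with a maximum of 50 returns every printed row; continuing the rule to 60 does not.

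| True rate | Pr(stop), printed and at 50 | Pr(stop) at 60 | Mean N at 50 | Mean N at 60 |
|---|---|---|---|---|
| 0.1 | 0.0006 | 0.0006 | 49.97 | 59.97 |
| 0.2 | 0.0225 | 0.0226 | 49.21 | 58.98 |
| 0.3 | 0.2215 | 0.2327 | 43.59 | 51.29 |
| 0.4 | 0.6869 | 0.7263 | 30.12 | 32.94 |
| 0.5 | 0.9597 | 0.9753 | 17.77 | 18.05 |

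The next boundaries under the same rule are 20/50 (posterior probability 0.928) and 22/55 (0.938). Neither is listed.

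**5. Table 11.** The futility rule was simulated 5,000 times with accrual of 2 per month, looks at each enrolment from patient 5 and a last look 6 months after the final entry. At a maximum of 50 and a 3-month median, Pr(stop) is 0.171 with mean N 44.1 (printed 0.1674 and 44.2). At 60 it is 0.174 with mean N 52.3. At a 2-month median, Pr(stop) is 0.855 at 50 (printed 0.855) and about 0.88 to 0.91 at 60, depending on whether that last look is included. At a 6-month median, mean N at 60 would be 59.7 (printed 49.5).

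**The case against.** The strongest reply is that the plan does have a default. The maximum is 60, precision is stated at 60, and the ten meet the same disease and prior-treatment criteria as everyone else, so all patients are analysed together. That is the natural reading, and it removes any claim that analysts are free to choose. It does not remove the concern, because this default is what enriches the estimate for carriers, and nothing shows that the effect was considered. It does stand that pooling shifts the patient mix rather than joining two separate diseases, since the initial cohort already contains carriers.

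Four stronger readings are tempting and not supported:

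- A reader might infer that Section 6 commits this trial to pooling. The sentence is conditional and most naturally concerns the future trial's analysis. It leaves this trial's analysis unsettled.
- A reader might infer that 43 + 10 = 53 contradicts 60. Both statements of 60 are ceilings, and 53 lies within them. 50 + 10 = 60 would fit the tables, but no text says so.
- A reader might infer that pooling would turn a failed trial into a success by passing 3 months. The documents set no success criterion on the final median and give no marker-group PFS.
- A reader might infer a practical safety gap after patient 45. The printed rule generates the later boundaries directly. Section 2 reports nine grade 3 toxicities and no grade 4, so at most 9 of 42 patients on that basis. Even if the next eight all had an event, 17/50 is below 20/50. Dosing delays over 14 days also count and are not reported, so this is reassurance rather than proof.

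**Conclusion.** The concern holds in two parts. First, Section 10 has no rule for the ten, and its default all-patient median over-represents carriers relative to the primary objective. The direction of the enrichment is certain if the ten are enrolled and treated and the other patients are not all carriers. Its effect on median PFS is unknown and may be zero, because every marker-group median used above is an assumption, as is exponential PFS. Exponential PFS with 42 events at 2.73 months would imply an interval of about 2.0-3.7, narrower than the reported 1.91-8.03, so the illustrated shifts are rough.

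Second, the printed monitoring tables belong to a 50-patient design. Table 12 matches exactly at 50, and Table 11 within simulation error. Moving to 60 changes the operating characteristics modestly, so this is mainly a matter of stated coverage. Both parts should be fixed; neither undermines the trial.

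**What to change.** - **Sections 10.2 and 10.6:** make the cohort enrolled without marker selection the primary PFS set, keeping carriers found in it. State its planned size and restate the credible interval for it. Report the criterion 15 patients separately, with their own posterior and Kaplan-Meier median and interval, whatever the result. Label any pooled estimate secondary.
- **Section 6:** name the trial whose final analysis is meant, and say what happens to these data if no further trial follows.
- **Sections 10.3 and 10.4:** either state that the rules and Tables 11 and 12 cover a maximum of 50, or rerun both for 60 and list 20/50 and 22/55. In either case, say whether monitoring includes the ten.

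**Cost:** wording changes, one extra results table and, if 60 is chosen, a rerun of two design programs. The primary interval is slightly wider, about 2.25-3.99 with 45 events against 2.31-3.89 with 55 at a 3-month median. If only the 42 treated patients form the primary set, 40 events give 2.22-4.06. The planned 35 events would be 35/50 = 70% of 50 patients or 35/42 = 83% of 42, against 35/60 = 58% of 60. The separate interval for the ten will be wide, for example 1.6-5.5 months with 8 events at a 3-month median.

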8. CRITERIA FOR REMOVAL FROM THE STUDY

Subjects who meet the following criteria should be discontinued from study treatment:

- Disease progression
- Intercurrent illness that prevents further administration of treatment
- Unacceptable adverse event(s) as determined by the treating physician
- Patient decides to withdraw from the study
- General or specific changes in the patient's condition render the patient unacceptable for further treatment in the judgment of the investigator.

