9.9 Time point evaluation

At each protocol specified time point, a response assessment occurs. Table 9 provides a summary of this for patients who have measurable disease at baseline. Table 10 provides a summary of this for patients with non-measurable (therefore non-target) disease.

Table 8: Response for measurable disease

Target Lesions	Non-target Lesions	New Lesions	Overall Response	Best Response for this Category also Requires
CR	CR	No	CR	≥ 4 weeks Confirmation
CR	Non-CR/Non-PD	No	PR	≥ 4 weeks Confirmation
CR	Not evaluated	No	PR	
PR	Non-PD or not all evaluated	No	PR	
SD	Non-PD or not all evaluated	No	SD	Documented at least once ≥ 6 weeks from baseline
Not All Evaluated	Non-PD	No	NE	NE
PD	Any	Yes or No	PD	No prior SD, PR or CR
Any	PD*	Yes or No	PD	
Any	Any	Yes	PD	

* In exceptional circumstances, unequivocal progression in non-target lesions may be accepted as disease progression. NE = inevaluable Note: Patients with a global deterioration of health status requiring discontinuation of treatment without objective evidence of disease progression at that time should be reported as “symptomatic deterioration.” Every effort should be made to document the objective progression even after discontinuation of treatment.

Table 9: Response for non-measurable disease

Non-target Lesions	New Lesions	Overall Response
CR	No	CR
Non-CR/Non-PD	No	Non-CR/Non-PD
Not all evaluated	No	NE
Unequivocal PD	Yes or No	PD
Any	Yes	PD

NE = inevaluable a 'Non-CR/non-PD' is preferred over 'stable disease' for non-target disease since SD is increasingly used as endpoint for assessment of efficacy in some trials so to assign this category when no lesions can be measured is not advised.

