10.3 Futility monitoring

For futility monitoring, we will monitor PFS using the methods of Thall et al and we will stop enrolling patients to the study if the median PFS is not likely to be longer than that from the historical data, which is around 3 months. Specifically, the trial will be stopped if $Pr(\lambda(E) > \lambda(S) | \text{data from the trial}) < 0.05$, where $\lambda(S)$ is the median PFS for historical patients under conventional care with an inverse gamma distribution $IG(58.25, 171.75)$, which corresponds to a mean of 3 months and a standard deviation of 0.4 month (variance = 0.16), the corresponding 95% CI of (2.32, 3.88) months. The prior for $\lambda(E)$ is assumed to be $IG(2.5625, 4.6875)$, corresponding to a mean of 3 months and a larger standard deviation of 4 (variance=16, the corresponding 95% CI is 0.72-10.67). Futility monitoring will start once 5 patients have been enrolled. Assuming an accrual rate of 2 per month and an additional follow-up of 6 months, the operating characteristics for the futility stopping rule under various scenarios are summarized in Table 11 below, with results based on 5000 simulations.

Table 11: Operating characteristics for futility monitoring

Median PFS (M)	Prob(Stop Early)	Mean No. of Patients (25%, 75%)
6	0.0058	49.5 (50, 50)
4.5	0.0216	49.1 (50, 50)
3	0.1674	44.2 (50, 50)
2	0.855	23.7 (10,37)
1.5	0.9992	12.3 (7, 16)

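### Symptomatic deterioration without a qualifying scan is not a PFS event, so the primary median PFS can be overstated, and no sensitivity analysis tests this

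*Combined protocol and SAP*

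**What the plan says.** **Stopping treatment.** Section 6: "Treatment will be continued until progression unless other reasons for study discontinuation occur as listed in section 8". Section 8 lists progression, intercurrent illness, unacceptable adverse events and withdrawal. It also lists a change in the patient whose "condition render the patient unacceptable for further treatment in the judgment of the investigator".

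**The label.** The note to Table 8 in section 9.9, repeated in 9.10, deals with "Patients with a global deterioration of health status requiring discontinuation of treatment without objective evidence of disease progression at that time". These patients are recorded as symptomatic deterioration, separately from progressive disease. Staff are told to keep trying to document objective progression after treatment stops.

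**The endpoint.** Section 10.2 defines PFS as a time "which is calculated as the time period from the date of treatment start to the date of disease progression or to the date of death". The earlier of the two counts. For all other patients the time runs "or to the last follow-up date if patients are alive without disease progression". Progression is judged by RECIST 1.1 (section 9.1). Section 10.6 gives a Bayesian posterior median with a 95% credible interval. No part of section 10 mentions symptomatic deterioration.

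**Scans around stopping.** Section 7 encourages an early scan on strong clinical suspicion. Section 7.1 asks for a tumour evaluation within 10 days of the decision to stop, unless imaging was done in the previous 4 weeks. Section 7.2 and footnote 6 of Table 7 give scans every 12 weeks (+/- 5) until progression or 12 months after first dose, and only while no other anti-cancer treatment is given. Section 7.3 follows survival about every 3 months, by medical record or telephone.

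**The concern.** A patient who stops because the cancer is clinically worsening, but whose decline is not confirmed on a scan, is still alive without disease progression under 10.2. PFS time keeps running until a later scan, death or last follow-up.

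The scan schedule narrows this gap without closing it. A patient stable on a scan who declines three weeks later needs no end-of-treatment scan. The next one may fall 12 to 17 weeks after the end-of-treatment visit, which is as long as the 3-month median being estimated. If new therapy starts, it need not happen at all. Censoring runs to last follow-up rather than last tumour assessment, so unscanned time can be counted as progression-free.

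This is a single-arm trial whose main result is an absolute median read against about 3 months. No control arm shares the error. The median reported for the first cohort in section 2 is 2.73 months, which is 3 - 2.73 = 0.27 month below that benchmark, so shifts of a few tenths of a month matter to the reading.

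**Working it through.** **Inputs from the documents.** Prior for the experimental median IG(2.5625, 4.6875). Historical median "IG(58.25, 171.75"), mean 3 months. Stop if the posterior probability that the experimental median exceeds the historical one is below 0.05. First look after 5 patients, accrual 2 per month, 6 months of further follow-up (section 10.3). Maximum of 50 patients, as Table 11 implies.

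**Inputs not in the documents (assumed).** Share s of patients who deteriorate with no progression recorded then: 10%, with 20% and 30% for range. Delay d until the event is recorded: 10 days (the end-of-treatment scan shows progression), 2 months on average (death), or 12 weeks (next off-treatment scan). The deterioration is taken to be true progression.

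**Model.** Exponential PFS. With E events and total follow-up F in months, the posterior for the median is IG(2.5625 + E, 4.6875 + ln2 x F).

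**Step 1: reproduce the plan's figures.** Simulated probability of an early futility stop against Table 11:

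| True median (months) | 6 | 4.5 | 3 | 2 | 1.5 |
|---|---|---|---|---|---|
| Table 11 | 0.0058 | 0.0216 | 0.1674 | 0.855 | 0.9992 |
| Simulated | 0.0080 | 0.0232 | 0.1658 | 0.8458 | 0.9988 |

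Section 10.2 states that with 35 events and a median of 3, "the 95% credible interval for the median PFS would extend from 2.1 to 4.2 months". The posterior shape is 2.5625 + 35 = 37.5625. Setting the posterior mean to 3 gives 2.17 to 4.14; setting the posterior median to 3 gives 2.21 to 4.21. Both agree within about 0.1 month, so the stated figures are sound and the model is a fair one for testing the concern.

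**Step 2: size of the shift by hand.** The exponential estimate of the median is close to ln2 x F / E. If a share s of N patients has its event recorded d months late, F rises by N x s x d. With nearly all events eventually seen, E stays near N. So

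rise in median = ln2 x s x d, approximately.

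For s = 0.10:
- 10 days = 0.33 month: 0.693 x 0.10 x 0.33 = 0.02 month
- death, mean 2 months: 0.693 x 0.10 x 2 = 0.14 month
- 12 weeks = 84/30.4 = 2.76 months: 0.693 x 0.10 x 2.76 = 0.19 month
- late edge of the scan window, 17 weeks = 119/30.4 = 3.91 months: 0.693 x 0.10 x 3.91 = 0.27 month

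**Step 3: simulation through the plan's posterior.** Final posterior median in months, base 2.00 to 2.01 at true median 2 and 2.95 to 2.96 at true median 3:

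| Share | Recorded | True median 2 | True median 3 |
|---|---|---|---|
| 10% | end-of-treatment scan, 10 days | 2.03 | 2.99 |
| 10% | death, mean 2 months later | 2.13-2.15 | 3.09-3.11 |
| 10% | scan 12 weeks later | 2.18-2.19 | 3.16 |
| 20% | end-of-treatment scan, 10 days | 2.05 | 3.01 |
| 20% | death, mean 2 months later | 2.27-2.29 | 3.23-3.24 |
| 20% | scan 12 weeks later | 2.38 | 3.35 |
| 30% | end-of-treatment scan, 10 days | 2.07 | 3.03 |
| 30% | death, mean 2 months later | 2.41 | 3.38 |
| 30% | scan 12 weeks later | 2.57 | 3.55 |

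At 10% the rise is 0.13 to 0.20 month for the two late routes and about 0.03 month when the end-of-treatment scan catches it. Even at 30% the latter is only 0.07 month. The formula and the simulation agree.

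**The case against.** The best defence is that the plan already works to document progression in these patients: early scans, an end-of-treatment evaluation within 10 days, 12-weekly scans, an explicit instruction to keep trying, and survival follow-up so that deaths are counted. Where these succeed the effect is negligible. That stands, and it is why the point is only that the median can be overstated. What it leaves is the waiver, the long scan interval and the cut-off at new therapy.

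A shift of 0.1 to 0.2 month is also small beside a credible interval of 2.1 to 4.2. That is true, but the interval describes sampling error and does not cover a bias in one direction.

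Decline is not always cancer progression, so recoding it can err downward. This stands, and is a reason for a sensitivity analysis rather than a new primary definition.

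Three stronger readings are tempting and are not supported:

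- A reader might infer that the first cohort already shows the bias, since disease control of 44% seems too low for a median of 2.73 months. The denominator is unclear: 18/42 = 42.9% and 19/42 = 45.2%, so neither rounds to 44%. Patients with only non-measurable disease who have not progressed are rated Non-CR/Non-PD (Table 9) and fall outside disease control while being properly progression-free. Section 2 does not say how the median was estimated, and cycles can slip by up to 3 weeks.
- A reader might infer that these patients are censored when they stop, which would give larger shifts. Section 10.2 censors at last follow-up, and survival follow-up continues, so that is not the plan's rule.
- A reader might infer that the fix also repairs futility monitoring. Late events do weaken the rule: at true median 2 with 10% affected, the stop probability falls from about 0.85 to about 0.73 (recorded at death) or 0.65 (12-week scan). But an added final analysis leaves section 10.3 unchanged, and section 2 reports 43 patients already enrolled.

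**Conclusion.** The concern holds as a possible overstatement of unknown size. Symptomatic deterioration is recorded but is not a PFS event, section 10 has no analysis that uses it, and the scan rules leave room for time after deterioration to count as progression-free. Any resulting error raises the median.

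If 10% of patients are affected, the median rises by about 0.1 to 0.2 month when the event is recorded at death (mean 2 months later) or at a scan 12 weeks later, and by about 0.1 month or less when the end-of-treatment scan documents progression. The shift grows in proportion to the share and the delay. These figures assume exponential PFS, 50 patients, and that the deterioration is real progression.

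It would be too strong to say that the primary median is overstated: the documents give neither the share nor the delay. Nor do they say whether the historical figure of about 3 months counted clinical progression, so bias in that comparison is unknown. Stops for toxicity or intercurrent illness are not part of this point. This is a cheap improvement and leaves the primary definition as it is.

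**What to change.** Keep progression or death as the primary definition in 10.2. Add to 10.6 one prespecified sensitivity analysis:

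- Count symptomatic deterioration, as labelled under 9.9 and 9.10, as a PFS event on the date of the decision to stop treatment. Leave stops for toxicity or intercurrent illness as they are.
- Run it through the same prior and posterior, and report the median with its 95% credible interval beside the primary result.
- Report how many patients are reclassified.
- State in the conclusion whether the reading against the 3-month benchmark depends on the coding. The plan sets no PFS success criterion, so this is a matter of reporting, not a pass/fail condition.

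The cost is SAP wording and one extra analysis of a status already recorded, with no new visits or scans. There are two downsides: the sensitivity median will be lower than the primary one if any patients are reclassified, and deterioration is an investigator judgement in an open-label trial. Fixing the rule before the final analysis limits the second.
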